**Proposed Treatment/Study Plan:**

Is treatment assignment randomized?  Yes  No

Is this a blinded or double-blinded study?  Yes  No

Allogeneic graft.

Peripheral blood (PB) or bone marrow (BM) progenitor cells may be used in this study.

Preparative Regimen.

Patients will be randomized to received either Flu/Bu or Flu/Clo/Bu and further stratified based on disease status, in complete remission (CR) or not in CR (NCR), at time of protocol entry/start of therapy.

Prior to initiating chemotherapy in this study, all toxicities from prior systemic chemotherapy must be resolved at least to grade 1. Flt3 or TKI inhibitors as well as intra-thecal therapy, nonmyelosuppressive agents, low dose cytarabine, hydroxyurea are permitted if indicated to control active leukemia, but must be stopped at least 5 days prior to administering the PK-test dose of IV Busulfan to avoid pharmacologic interference with IV Bu.

Acetaminophen should not be used between D-10 (starting 24 hours before the test dose of IV Bu) and D0. Other drugs known to interfere with the metabolism of Flu and/or Bu should not to be concomitantly used during the chemotherapy administration up to and including the day of transplantation. day following the stem cell transplant procedure.

Busulfan test dose:

The Busulfan test dose can be administered within 10 days prior to admission as an outpatient or as an inpatient.

Pharmacokinetic-guided (PK-guided) treatment: The Bu "test dose" of 32 mg/m^2 will be based on actual body weight. This Bu dose will be given IV over 45 minutes (for patients up to age 60) and over 60 min (for patients ages 61-70) by controlled-rate infusion pump.

Busulfan adjusted dose determined to achieve a systemic exposure represented by an average daily AUC of 6000 µMol-min ± 5% for the entire 4-day treatment period is administered to all patients up to age 60 who have ECOG performance status 0 or 1 or Karnofsky/Lansky 90-100. The target AUC is 4,000 µMol-min ± 5% for patients ages 61-70 and younger patients with ECOG performance status 2 or Karnofsky 60-80. If pharmacokinetic analysis cannot be completed for any reason, Bu will be given in a dose of 130 mg/m^2 dose (for the target AUC 6000) and 100 mg/m^2 (for target AUC 4000).

Fludarabine/ Clofarabine/ Busulfan

Fludarabine administration:

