#### **Statistical Considerations:**

**Treatments and Outcomes.** This is phase III clinical trial of allogeneic stem cell transplantation for AML/MDS patients, having age between 3 and 70 years, who are either in complete remission or not in CR (NCR). All patients will be randomized between two preparative regimens. Both regimens have been studied in recent MDACC trials and found to be adequately safe and effective, warranting this randomized comparison. The first preparative regimen (FluBu) consists of fludarabine (dose = 40 mg/m^2) + intravenous (IV) busulfan using a subgroup-specific PK targeted dose (target dose = 6000 micromolar x minute in patients up to age 60 with ECOG performance status 0 or 1 or 4000 for patients 61-70 years of age or performance status 2). The second preparative regimen (FluCloBu) consists of fludarabine (dose = 10 mg/m^2) + clofarabine (dose = 30 mg/m^2)+ IV busulfan dosed in the same manner. The primary endpoint will be T = progression-free survival (PFS) time, defined as the time from date of transplant to death from any cause or disease progression. Secondary endpoints will include overall survival (OS) time, and the indicator G100 that the patient has grade 3 or 4 acute graft-versus-host disease at any time during the first 100 days post transplant.

**Design and Trial Conduct.** 250 patients will be entered. The two preparative regimens, FB and FCB, will be compared in terms of PFS time using a group sequential design(38) with two-sided O'Brien-Fleming boundaries, with up to two interim tests and one final test, having overall Type I error .05 and power .90

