to detect an improvement of  $\text{Pr}(T > 12 \text{ months})$  from a null value of .56 to a target value of .71, equivalently, to detect a change in median PFS from 14.35 to 25.29 months. The null value of  $\text{Pr}(T > 12 \text{ months})$  was determined by assuming that  $\text{Pr}(T > 12 \text{ months} | \text{CR}) = .65$  and  $\text{Pr}(T > 12 \text{ months} | \text{NCR}) = .50$ , based on experience with Flu + IV Busulfan, and the assumption that  $\text{Pr}(\text{CR}) = .40$ , giving null  $\text{Pr}(T > 12 \text{ months}) = .40 \times .65 + .60 \times .50 = .56$ . The decision boundaries, in terms of the standardized log rank statistic, are  $+/-.3.7103$ ,  $+/-.2.5114$ ,  $+/-.1.993$  to be applied when, respectively, 52.16, 104.31, and 156.46 events (death or progression) have been observed in both arms combined. The Pocock-Simon method will be used to dynamically balance the randomization on the binary (CR, NCR) indicator, using the Department of Biostatistics Clinical Trial Conduct website.

**Data Analyses.** Kaplan-Meier plots will be used to estimate the unadjusted OS and PFS time distributions. Time-to-event regression analyses will be used to evaluate the ability of treatment arm and patient covariates to predict OS and PFS, with the model underlying model chosen based on preliminary goodness-of-fit analyses of the data. The rate of 100 day severe GvHD will be estimated by tabulations and computation of posterior credible intervals, overall and within the CR and NCR. To account for the treatment and baseline covariates,  $\text{Pr}(\text{GvHD within 100 days})$  will be estimated using logistic regression.

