**Protocol Monitoring:**

Does this protocol have a schedule for interim and final analysis? Yes

Provide a summary or schedule of interim analysis.

The two preparative regimens, Flu-Bu and Flu-Clo-Bu, will be compared in terms of PFS time using a group sequential design(38) with two-sided O'Brien-Fleming boundaries, with up to two interim tests and one final test, having overall Type I error .05 and power .90 to detect an improvement of  $\text{Pr}(T > 12 \text{ months})$  from a null value of .56 to a target value of .71, equivalently, to detect a change in median PFS from 14.35 to 25.29 months.

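### State that the log-rank test of PFS is stratified by remission status at all three looks; the gain is small, about 0.8 point of power if the hazard ratio is the same in CR and NCR

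*Combined protocol and SAP*

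**What the plan says.** Statistical Considerations makes PFS the primary endpoint, counted from transplant until the patient progresses or dies. The paragraph on design and trial conduct states that "250 patients will be entered" and sets a three-look, two-sided O'Brien-Fleming design with overall Type I error .05 and power .90. It then continues: "The decision boundaries, in terms of the standardized log rank statistic, are" ±3.7103, ±2.5114 and ±1.993, applied at 52.16, 104.31 and 156.46 events. The word log-rank carries no qualifier there.

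Remission status enters the plan in three other ways:

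- **Randomisation.** "The Pocock-Simon method will be used to dynamically balance the randomization on the binary (CR, NCR) indicator". Proposed Treatment/Study Plan adds that patients are "further stratified based on disease status, in complete remission (CR) or not in CR (NCR), at time of protocol entry/start of therapy". This describes allocation, not the test.
- **Planning assumptions.** The null 12-month PFS of .56 is built from .65 in CR, .50 in NCR and a CR share of .40.
- **GvHD.** The 100-day rate is to be reported overall and by remission status.

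Protocol Monitoring repeats the design ("The two preparative regimens, Flu-Bu and Flu-Clo-Bu, will be compared in terms of PFS time using a group sequential design(38") without naming the test. The Data Analyses paragraph says "Time-to-event regression analyses will be used to evaluate the ability of treatment arm and patient covariates to predict OS and PFS". The form of that regression is to be "chosen based on preliminary goodness-of-fit analyses of the data", and it is not connected to the boundaries.

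**The concern.** When allocation is balanced on a prognostic factor and the test ignores it, two small things happen. The statistic varies less between trials than its variance estimate assumes, so the test is conservative. And if the hazard ratio is the same in both strata, the pooled comparison is pulled slightly towards no effect. Stratifying the log-rank by the same factor removes both, using data the trial already holds.

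The second issue is pre-specification. The plan stratifies the allocation, so a reader could expect a stratified test; the words of the boundary sentence suggest a plain one. The two forms can give different answers on the same data, and this is a phase III comparison with three looks. The form should not be open when results are seen.

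**Working it through.** **1. The plan's own figure.** Under exponential PFS, HR = ln(.71)/ln(.56) = .591.

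- The printed boundaries at the printed event counts give an overall two-sided Type I error of .0500.
- With drift |ln HR|·√D/2 = .5265 × √156.46/2 = 3.29 (Schoenfeld), group-sequential power is .906.
- With drift √D·(1−HR)/(1+HR) = 12.51 × .4093/1.5907 = 3.22 (Freedman), it is .893.

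The stated .90 therefore reproduces. The printed medians imply a different ratio, 14.35/25.29 = .567, at which power would be .941 or .930. The design thus rests on .56 against .71.

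**2. How prognostic the plan assumes CR to be.** The NCR:CR hazard ratio is ln(.50)/ln(.65) = 1.61.

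**3. Which within-stratum effects match the target.** The documents give none, so these are assumptions.

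- Same HR .591 in both strata: .4 × .65^.591 + .6 × .50^.591 = .7086. HR .587 gives .7100.
- Equal 15-point improvement: .4 × .80 + .6 × .65 = .71. The HRs are ln(.80)/ln(.65) = .518 in CR and ln(.65)/ln(.50) = .621 in NCR.
- Other unequal effects: the CR hazard ratio is set and the NCR one solved so that the mixture is .71.

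**4. Simulation.** There are 250 patients, accrued uniformly over 250/7 = 35.7 months, 40% in CR, with exponential PFS within stratum. Looks are at 52, 104 and 156 events, with the printed boundaries. Both log-rank forms are computed on the same trials, 100,000 per case. Power counts crossings in favour of the three-drug arm. Further assumptions: 1:1 allocation, a biased coin of .8 within CR/NCR, and no dropout.

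| Case (HR in CR / NCR) | Plain | Stratified | Difference |
|---|---|---|---|
| Same HR, .591 / .591 | .892 | .900 | +.008 |
| Same HR, .587 / .587 | .899 | .906 | +.008 |
| Equal 15 points, .518 / .621 | .908 | .909 | +.001 |
| Larger effect in CR, .46 / .65 | .916 | .910 | −.006 |
| Larger effect in CR, .37 / .70 | .934 | .913 | −.021 |
| Larger effect in NCR, .67 / .55 | .890 | .903 | +.013 |
| Larger effect in NCR, .73 / .52 | .886 | .901 | +.015 |
| Half the assumed gap (control .605 / .53) | .901 | .902 | +.001 |
| CR not prognostic (control .56 / .56) | .9001 | .8985 | −.002 |

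Differences are taken before rounding. For the same-HR case the paired standard error is .0004. Type I error is .047 plain and .051 stratified (standard error .0007). At the target effect the two forms reach different conclusions in 1.8% to 2.0% of trials.

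**5. Stability.**

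- Accrual of 5 or 10 a month gives a gain of .0085 or .0075. A biased coin of .9 still gives .008.
- Separate simulations at HR .591 gave .895 against .903 (60,000 trials) and .888 against .897 (20,000 trials). Their Type I errors were .046 against .050 and .044 against .048.
- For the equal 15-point case, these separate simulations put the gain at 0.0 point (30,000 trials) and 0.4 point (20,000 trials).
- If CR were more prognostic than the plan assumes (12-month control PFS .75 and .43, an assumption), the gain at HR .587 is about 4.8 points (.859 against .907).

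**6. Effect on the estimate.** In one data set of 2,000,000 simulated patients with a true within-stratum HR of .587, cut at the same event fraction (156/250), the plain Cox hazard ratio is .594 and the stratified one .587.

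**The case against.** The strongest reply is that the plan does name its test. An unqualified log-rank, with events counted in both arms combined and one overall target of .56 to .71, ordinarily means a plain log-rank on all patients. Where the plan wants remission status used, it says so. That test is valid and has its stated power. This all stands, so the point is not an error in alpha, power or event counts.

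The reply also notes that the 0.8 point needs a common hazard ratio. Adding 15 points in each stratum meets the .71 target exactly and leaves almost nothing to gain. A larger effect in CR turns the gain into a loss. This stands too: the documents do not tell us which case holds, and the power argument is conditional.

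The 2% disagreement matters only if someone could choose between the tests after seeing results. Stating either form would close that route. But the protocol leaves the form unstated, and of the two, the stratified test follows the randomisation and uses the prognostic difference that the plan itself assumes. A stratified Cox hazard ratio changes the estimate slightly (.587 rather than .594), but it makes the estimate match the test. The planned regression is no substitute, because its model is chosen from the data and it plays no part in the boundary decision.

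**Conclusion.** The concern holds, as a small efficiency and pre-specification point. The documents do not say whether the boundary test is stratified by CR/NCR. Under the plan's inputs and a common hazard ratio, stratifying adds about 0.8 point of power and brings Type I error from about .047 to about .05. Across the unequal effects examined that keep the .71 target, the change runs from +1.5 to −2.1 points; if CR is not prognostic it is about −0.2 point. These sizes rest on exponential PFS within stratum, 1:1 allocation, no dropout and the assumed within-stratum hazard ratios. The need to fix the form in advance does not depend on which of these cases is true.

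**What to change.** In the design paragraph of Statistical Considerations, state before the first look that both interim tests and the final test use the log-rank statistic stratified by CR/NCR as recorded at randomisation. The boundaries and event counts stay as they are. Naming the randomisation record also settles which of the two time points in Proposed Treatment/Study Plan (entry or start of therapy) the test uses. Report the hazard ratio from a Cox model stratified by CR/NCR. Keep the plain log-rank as a sensitivity analysis that is not compared with the boundaries.

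The cost is a line of wording, with no new data and no more patients. The price in power could be about 0.2 point if remission status turns out not to be prognostic, about 0.6 point if the effect is larger in CR (.46 / .65), and about 2 points in the more extreme case (.37 / .70).

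### The primary PFS log-rank test names no strata; stratifying it by CR/NCR, the factor already used to balance allocation, is a free but small gain in power

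*Combined protocol and SAP*

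**What the plan says.** **The decision test.** In Statistical Considerations (Design and Trial Conduct), PFS is compared at up to three looks with O'Brien-Fleming boundaries: "The decision boundaries, in terms of the standardized log rank statistic", are 3.7103, 2.5114 and 1.993 in absolute value, applied at 52.16, 104.31 and 156.46 events. No stratum or covariate is attached to that statistic. Protocol Monitoring repeats that the regimens "Flu-Bu and Flu-Clo-Bu, will be compared in terms of PFS time" and adds nothing on this point.

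**Allocation.** Proposed Treatment/Study Plan says that patients are randomised and "further stratified based on disease status, in complete remission (CR) or not in CR (NCR". Statistical Considerations gives the mechanism: "The Pocock-Simon method will be used to dynamically balance the randomization on the binary (CR, NCR) indicator". Both statements describe how treatment is assigned.

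**The prognostic assumption.** The control value of .56 for 12-month PFS is built from .65 in CR (40% of patients) and .50 in NCR (60%), "based on experience with Flu + IV Busulfan".

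**Adjustment elsewhere.** The Data Analyses paragraph states: "Time-to-event regression analyses will be used to evaluate the ability of treatment arm and patient covariates to predict OS and PFS". It does not list the covariates, chooses the model after goodness-of-fit checks, and does not tie the result to the boundaries. CR/NCR is named in an analysis only for the estimation of severe GvHD.

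**The concern.** The plan treats CR/NCR as prognostic and balances the arms on it, but its decision test does not use it.

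This has two consequences. First, balancing makes the arms more alike on a prognostic factor than simple randomisation would, while the unstratified log-rank variance takes no account of that. The statistic then varies less than its standardisation assumes, so the test is slightly conservative. Second, pooling patients with different hazards slightly dilutes the treatment effect that the unstratified statistic measures.

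A stratified test avoids both. What is at stake is a small amount of power that could be had without more patients, events or follow-up. It also helps to have the exact form of the primary test written down before the first look.

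**Working it through.** **1. Reproduce the plan's figures.**
- Control mixture: .40 × .65 + .60 × .50 = .56, as stated.
- Exponential median at .56: 12 × ln 2 / (−ln .56) = 14.35 months, as stated, so exponential PFS is a fair reading of the design.
- Target hazard ratio: ln(.71)/ln(.56) = .5907.
- Fixed-design events (Schoenfeld, 1:1): 4 × (1.960 + 1.282)² / (ln .5907)² = 151.6.
- With the stated boundaries, 153.4 events give power .90. The stated 156.46 is 2% higher (156.46/153.4 = 1.02).
- Integrating the stated boundaries at the stated event counts gives overall type I error .0500 and power .905.

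The event target follows from .56 versus .71. The printed medians would imply a hazard ratio of 14.35/25.29 = .567 and about 132 events, so I work from the 12-month figures.

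**2. Strength of the balancing factor.** NCR to CR hazard ratio: ln(.50)/ln(.65) = 1.61. Expected stratum sizes: 250 × .40 = 100 CR and 250 × .60 = 150 NCR.

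**3. Simulate both tests on the same trials.**
- From the documents: 250 patients, 7 entered per month, Pr(CR) = .40, control 12-month PFS .65 and .50, and the stated boundaries. Looks were at 52 and 104 events and finally at 156 or 157.
- Assumed: exponential PFS, 1:1 allocation, the same treatment hazard ratio in both strata, and a biased coin of .8 for the Pocock-Simon step.
- The within-stratum hazard ratio h solves .40 × .65^h + .60 × .50^h = .71, giving h = .587.

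| Runs per setting | Power, unstratified | Power, stratified | Type I error, unstratified | Type I error, stratified |
|---|---|---|---|---|
| 60,000 | .8984 | .9062 | .0469 | .0512 |
| 40,000 | .897 | .905 | .047 | .051 |
| 24,000 null, 12,000 alternative | .898 | .905 | .045 | .049 |
| 15,000 | .898 | .905 | .045 | .050 |
| 15,000 | .901 | .909 | .049 | .052 |

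The standard error of type I error is about .001 at 60,000 runs and .002 at 15,000, so the last row agrees with the others within noise. In the 60,000 runs the gain is .0078 (SE .0006): only the stratified test rejects in .0135 of trials and only the unstratified test in .0057.

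**4. Why the unstratified test is conservative.** In the 24,000 null runs the final standardised statistic had standard deviation .975 unstratified and .993 stratified, against a nominal 1. At h = .587 its mean was 3.226 and 3.294 in absolute value.

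**5. Convert the gain to events.** The normal density near power .898 is .177, so .0078/.177 = .044 on the Z scale. With an expected Z of about 3.233, and information proportional to Z², 2 × .044/3.233 × 156 = 4.2 events.

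**6. Sensitivity.**
- With the within-stratum hazard ratio fixed at .591, power goes from .8925 to .8997 (+0.7 points), and from .891 to .898 in 15,000 runs. A run of 12,000 gave .8913 to .9015 (+1.0, SE √(.0227/12,000) = .0014), about two standard errors higher.
- If CR/NCR were not prognostic (.56 in both strata, an assumption), power would be .898 unstratified and .896 stratified, a cost of about 0.2 points.
- If it were more prognostic (.75 and .433, also an assumption), power would be .850 and .899.

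**The case against.** The strongest reply is that nothing is left open. A log-rank statistic with no strata named is ordinarily the unstratified one, and the design fits that reading: the two stratum values are collapsed into a marginal .56, and events are counted over both arms combined. Where the authors want results by CR/NCR, as for GvHD, they say so. The plan asks for type I error .05 and power .90, and the unstratified test delivers about .047 and .898. A regression with covariates is planned besides.

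Most of this stands. The unstratified reading is the natural one, and the shortfall is small. The regression answers the point only in part, because it neither names CR/NCR nor drives the decision.

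A reader might infer more than the documents support:
- **That the test is invalid or biased.** It is neither. It errs slightly on the conservative side.
- **That the silence inflates type I error.** If the version were picked after seeing both results, simulated type I error would be .055, but no section provides for such a choice.
- **That stratification is already intended for the test.** The wording in the treatment plan concerns assignment to regimen only.
- **That several points of power are being lost.** That needs a CR/NCR effect stronger than .65 versus .50, for which the documents give no basis.

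**Conclusion.** The point holds as a free improvement of minor severity. The decision test uses no strata although allocation is balanced on CR/NCR and the plan itself treats that factor as prognostic. Under the plan's own figures, stratifying takes type I error from about .045–.047 to about .05 and power from about .898 to about .905. The gain is 0.7 to 0.8 points, or roughly 4 of 156 events.

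The two tests would reach different decisions in about 1.9% of trials at the target effect and 1.3% under the null, which is reason enough to name the version in advance. The sizes rest on exponential PFS, a common hazard ratio in the two strata, 1:1 allocation and a biased coin of .8. The direction does not depend on the exact values so long as CR/NCR is about as prognostic as the plan assumes.

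**What to change.** Add one sentence to Statistical Considerations (Design and Trial Conduct) and repeat it in Protocol Monitoring, before the first interim look. For example: *At each of the three looks, the boundary is applied to the log-rank statistic stratified by disease status (CR, NCR), using the value recorded for the Pocock-Simon allocation.*

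Keep the boundaries, the event counts and the 250 patients. The factor is already recorded for allocation, and strata of about 100 and 150 patients are ample for a stratified test. The only statistical cost is about 0.2 power points, and only if CR/NCR turned out not to be prognostic at all. If the sponsor prefers the unstratified test, saying so explicitly would also settle the form of the test, at the small loss shown above.

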#### **Estimated Accrual:**

Total Accrual at MDACC: 250  
Estimated monthly accrual at MDACC: 7

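### Does tying the final test to 156.46 events, with no latest date, put the primary analysis at risk?

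*Combined protocol and SAP*

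**What the plan says.** Statistical Considerations (Design and Trial Conduct) states that "250 patients will be entered" and that PFS will be compared with "two-sided O'Brien-Fleming boundaries, with up to two interim tests and one final test", "having overall Type I error .05 and power .90". The boundaries on the standardized log-rank scale are 3.7103, 2.5114 and 1.993, "to be applied when, respectively, 52.16, 104.31, and 156.46 events (death or progression) have been observed in both arms combined". The effect to be detected is a rise in 12-month PFS "from a null value of .56 to a target value of .71". Estimated Accrual gives "Estimated monthly accrual at MDACC: 7".

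Protocol Monitoring asks "Does this protocol have a schedule for interim and final analysis? Yes" and then restates the design. Neither section gives a minimum follow-up, a latest date, or a rule for the final boundary at a different event count. A DSMB is named.

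**The concern.** The final test is defined by an event count alone, and that count is a large share of a fixed sample. Under constant hazards every patient eventually has an event, so any count up to 250 is reached. If some patients never progress or die within any practical follow-up, events run out. The document reports no PFS experience beyond 12 months, so it does not exclude this.

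The problem would also be lopsided, because a better regimen yields fewer events. The count would be hardest to reach when the experimental arm works. Read literally, the trial would then have only its two interim tests, with combined power of .57. Otherwise someone would choose the date of the final test after data had accumulated, with no written rule.

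**Working it through.** **Inputs.** From the document: 250 patients, 7 a month, 12-month PFS .56 and .71, looks at 52.16, 104.31 and 156.46 events, boundaries 3.7103, 2.5114 and 1.993. Assumed: 1:1 allocation (the ratio is not stated), uniform accrual, proportional hazards, no dropout.

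**1. The plan's own figures.**
- Hazard ratio = ln(.71)/ln(.56) = .591.
- Events for a fixed design (Schoenfeld, two-sided .05, power .90) = 4(1.960 + 1.282)²/(ln .591)² ≈ 152. With the three stated boundaries, 153.3 events give power .90, so 156.46 is slightly generous.
- Recursive integration over the stated boundaries gives cumulative alpha .0002, .0121, .0500 and cumulative power .035, .571, .905. The stated error rates hold.
- The target median of 25.29 months does not match .71 at 12 months, which implies 12 × ln 2/(−ln .71) = 24.29. The event count follows the .56/.71 pair, so this does not matter here.

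**2. When the count is reached under constant hazards.** Accrual takes 250/7 = 35.7 months. Expected events reach 156.46 at month 46.3 under the target effect (10.6 months after the last entry) and at month 40.7 with no effect (5.0 months after).

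**3. What a plateau would do.** Let control PFS be S₀(t) = c + (1 − c)exp(−λt) with S₀(12) = .56, and experimental PFS S₀(t)^.591. Then

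maximum expected events = 125(1 − c) + 125(1 − c^.591).

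This equals 156.46 at c = .278. With no effect it is 250(1 − c), so c = 1 − 156.46/250 = .374. At intermediate hazard ratios of .7 and .8 the thresholds are .309 and .333.

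The rule needs a whole number of events, so 157. The chance of ever having 157, from the sum of Bin(125, 1 − c) and Bin(125, 1 − c^HR):

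| Control plateau c | Maximum expected events, target effect | Chance of 157, target effect | Chance of 157, no effect |
|---|---|---|---|
| .20 | 176.7 | .998 | 1.00 |
| .25 | 163.6 | .83 | 1.00 |
| .30 | 151.1 | .24 | .99 |
| .35 | 139.0 | .01 | .79 |
| .40 | 127.2 | <.001 | .20 |

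The second look, at 104.31 events, is below the expected maximum in every row.

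**4. What is lost if the final test is simply run late.** Take a final test 24 months after the last entry (month 59.7) under the target effect. The same recursion, with the third look at the expected event count, gives:

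| Control plateau c | Expected events | Alpha at 1.993 | Power at 1.993 | Boundary for alpha .05 | Power at that boundary |
|---|---|---|---|---|---|
| .25 | 152 | .0497 | .898 | 1.99 | .898 |
| .30 | 144 | .0491 | .880 | 1.985 | .881 |
| .35 | 134 | .0484 | .858 | 1.978 | .861 |
| .40 | 125 | .0475 | .830 | 1.970 | .836 |

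Using 1.993 at fewer events is slightly conservative, and recomputing the boundary gains at most about half a point of power.

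**5. Whether a written cap is free.** Not entirely. Keep hazards constant and the ratio at .591, but suppose control 12-month PFS is .70 (an assumption). Then 156.46 events arrive 26.4 months after the last entry, and a 24-month cap would stop the trial at about 151. At .75, a 24-month cap stops it at about 133 events, and a 36-month cap falls just short at 155.6.

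**The case for a change.** The best argument for acting is that a fallback costs only wording, needs no extra patients, and removes discretion over the date of the final analysis. It would guard the case where the trigger is least reachable, namely a working regimen with durable responders: at a 30% plateau the chance of reaching 157 is .99 with no effect but .24 at the target effect. Loss to follow-up would narrow the margin. If 5% or 10% of patients gave no event information (assumed figures), the 27.8% threshold would fall to about 24.6% or 21.1%.

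The arithmetic stands, and so does the observation that no date is written down. Three things limit its force. The plateau is not in the document, whose .56 at 12 months and median of 14.35 months fit an exponential curve; nothing there favours a plateau of 25 to 40% over one of 0 to 20%. The power of .57 applies only if no final test is ever run, whereas the plan commits to one ("with up to two interim tests and one final test, having overall Type I error .05 and power .90"). And a cap on a whichever-comes-first basis can itself end a trial that would have reached its planned events, as step 5 shows.

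The public text is also headed as an abstract and points to a treatment scheme that it does not contain, so the absence of a follow-up rule here is weak evidence that none exists.

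**Conclusion.** No change is needed. Under the assumptions on which the trial was sized, the event count is reachable about 11 months after the last entry and the power statement is right. Failure to reach it requires an unreported control plateau above about 28% with the full target effect, or about 37% with none. In that case a late final test at the stated boundary still controls alpha (.0475 to .0497) and keeps power between .83 and .90 for plateaus of 40% down to 25%. That is a loss of roughly 1 to 8 points from .905.

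What remains is an unwritten timing detail. If events slowed, the statistician and the DSMB would fix a cutoff from the pooled event count and apply the final boundary, recomputed or not. This rests on 1:1 allocation, proportional hazards, little dropout, and a cutoff chosen without sight of the treatment difference. A sentence on timing would be harmless if any cap were long, but it is optional.
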